## **8.1. Analysis Sets**

### **8.1.1. Screening Analysis Set**

The Screening Analysis Set is defined as all subjects who give written informed consent and have entered screening. Analyses will be restricted to presentation of baseline data and reasons for non-participation as contrasted to those enrolled and received study drug.

### **8.1.2. Safety Analysis Set**

The Safety Analysis Set is defined as all enrolled subjects who were administered the single dose of study drug.

### **8.1.3. Pharmacokinetic Analysis Set**

The Pharmacokinetic Analysis Set is defined as all subjects who received a dose of cytisine and have evaluable pharmacokinetic data.

## **8.2. Subject Disposition**

The number and percentage of subjects who meet study analysis set requirements will be presented, along with number and percentage of subjects who prematurely withdrew. Reasons for withdrawal will be included.

## **8.3. Demographic and Other Baseline Characteristics**

Subjects demographic data (except date of birth) and other baseline characteristics will be collected at screening and will be listed and summarized descriptively for all subjects by treatment and overall. The data in the summary will include age (years), sex, race, height (cm), weight (kg) and body mass index (BMI,  $\text{kg}/\text{m}^2$ ).

## **8.4. Medical and Smoking History**

Medical history will be collected at screening and coded using the MedDRA dictionary version 21.1 or higher. Coding includes system organ class (SOC) and preferred term

(PT). Medical history events will be listed for all subjects. Frequencies of medical history events will be presented by SOC and PT, by treatment and overall.

Smoking history will be collected at screening and will be listed and summarized descriptively for all subjects by treatment and overall. The data in the summary will include duration (years) of smoking, average number of cigarettes smoked per day during the last 30 days, whether subject ever attempted to quit smoking (Yes, No). In addition, the following will be summarized for subjects who had ever attempted to quit smoking: number of previous quit attempts, time (months) since most recent quit attempt and smoking cessation treatments used. The summary of smoking cessation treatments will report the number and percentage of subjects that used each treatment, as well as the number (%) of subjects that used any prior nicotine replacement therapy (i.e., used nicotine gum or nicotine patch or nicotine nasal spray or nicotine inhaler).

Expired CO level (ppm) will be measured at screening. These data will be listed for all subjects and summarized for all subjects by treatment and overall.

## **8.5. Dosing**

Study product administration dates and times will be listed.

## **8.6. Protocol Deviations**

Protocol deviations will be listed.

## **8.7. Safety Assessments**

### **8.7.1. Adverse Events**

Clinically significant abnormalities will be reported as AEs. Adverse events will be coded using the MedDRA dictionary version 21.1 or higher. Coding includes system organ class (SOC) and preferred term (PT). The following information recorded or computed is used for the description of the AEs: reported Term; SOC and PT by MedDRA coding; start date, start time, end date and end time; seriousness; severity (intensity); relationship (causality); action taken; outcome. AE duration and time to AE onset will be derived and presented in the subject data listings.

TEAEs will be presented by dose level. TEAEs are defined as AEs not present prior to administration of investigational product, or AEs present before administration of investigational product that worsen after the subject received the investigational product. A separate listing of SAEs will be presented, if applicable. Frequencies of TEAEs will be presented by SOC and PT, by Test product and placebo and overall.

TEAEs of which the relationship to the test drug was classified as ‘possible’, ‘probable’ and ‘definite’ will be regarded as “related”, while TEAEs that are classified as ‘not related’ or ‘unlikely’ will be regarded as “not related”.

Frequencies of TEAEs will also be reported by severity class (Mild, Moderate, or

Severe) and by investigational product and dose, for all causalities and for “related” events.

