#### 3.2. Reporting and Deliverables

The CSR will be written using the Achieve's template. Tables, Figures and Listings (TFLs) will be prepared as described in the TFL shells within this SAP. In-text Tables and Figures will be included in the main body of the CSR. After review by the Sponsor, the TFLs will be finalized.

Before performing the analysis, all data collected will be integrated into a common repository, using SAS 9.4 (SAS Institute Inc, Cary, NC, USA). Derived analysis datasets will be generated in accordance to CDISC. ADaM compliant datasets will be delivered to the Sponsor.

[figure not shown]

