## 5. STUDY DESIGN OVERVIEW

### 5.1. Study Design

[figure not shown]
This was a single-center, double-blind, randomized, placebo-controlled, single dose-escalation, Phase 1 clinical study conducted in male or female adults who were in good general health and were current daily cigarette smokers, under fasting conditions.

Nine dose levels were pre-planned under version 5.0 of Protocol ACH-CYT-08: 6 mg, 9 mg, 12 mg, 15 mg, 18 mg, 21 mg, 24 mg, 27 mg and 30 mg. The starting dose was 6 mg cytisine (single oral dose) in Cohort 1. The study was escalated up to the cytisine dose of 30 mg in Cohort 9 without showing any of the predefined stopping criteria. Within each dose level, subjects were randomly assigned to receive a single oral dose of cytisine or placebo in a 3:1 ratio (6 cytisine:2 placebo).

Upon completion of a cohort, a safety review was performed by the Principal Investigator (PI) and two independent Data Safety Monitors (DSMs) on unblinded data. The PI and DSMs conjointly decided whether dose escalation into the next cohort was to be allowed.

Table 1 presents an overview of study design.

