## 8. STATISTICAL METHODS

The statistical analysis and TFLs will be done using SAS® for version 9.4.

PK parameters for cytisine ( $C_{max}$  and  $T_{max}$ ) will be estimated using non-compartmental analysis (NCA) in Phoenix® WinNonlin® version 8.1 (Pharsight Corp., Mountain View, CA).

Summaries of demographics, baseline characteristics and safety endpoints will be provided for the Safety Analysis Set, defined as all subjects who received a single dose of cytisine or placebo.

Unless otherwise indicated, numerical variables will be summarized using: number of observations (n), arithmetic mean, standard deviation, coefficient of variation (CV%), median and range (minimum and maximum). Categorical variables will be summarized with number of subjects and percentage within a treatment (dose level). Descriptive statistics will be presented with the same precision as the original data, i.e, the same number of decimals or significant digits.  $T_{max}$  is stated with the same number of significant digits as the actual sampling time. Baseline for post-dose assessments is defined as the last observation recorded before dose. Summaries will be provided for each dose level/treatment (Placebo; 6.0 mg cytisine; 9.0 mg cytisine, etc.). Unless otherwise indicated, no statistical comparisons between the cohorts are planned.

Unscheduled measurements will be listed in the individual data listings. With the

exception of baseline or unscheduled measurements performed due to an error at the scheduled measurement (e.g. equipment failure), unscheduled measurements will be excluded from the descriptive statistical analysis.

No imputation of missing data will be done, except for missing dates and/or times required for the calculation of AEs' time to onset and duration (e.g. see Section 8.7.1) and for plasma concentrations below the lower limit of quantification (LLOQ) (see Section 8.8).

Assessments for trends in dose-limiting adverse events or  $C_{max}$  levels in relationship to BMI categories/levels and baseline Nicotine Metabolite Ratio (NMR) may be explored.

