14.2 SAFETY DATA	
14.2.1	Treatment Emergent Adverse Events
14.2.1.1	Adverse Events Leading to Discontinuation or Withdrawal
14.2.1.2	Listings of Serious Adverse Events
14.2.1.3	Summary of Treatment Emergent Adverse Events – All Causalities
14.2.1.4	Summary of Treatment Emergent Adverse Events - Related
14.2.1.5	Summary of Treatment Emergent Adverse Events by Severity –

	All Causalities
14.2.1.6	Summary of Treatment Emergent Adverse Events by Severity – Related
14.3 PHARMACOKINETIC DATA	
14.3.1	Deviations from Blood Sampling Schedule
14.3.1.1	Deviations from Blood Sampling Schedule
14.3.1.2	Missing Blood Samples
14.3.2	Plasma Concentrations
14.3.2.1	Cytisine 6 mg: Individual Data and Descriptive Statistics of Plasma Concentrations
14.3.2.2	Cytisine 9 mg: Individual Data and Descriptive Statistics of Plasma Concentrations
14.3.2.3	Cytisine 12 mg: Individual Data and Descriptive Statistics of Plasma Concentrations
14.3.2.4	Cytisine 15 mg: Individual Data and Descriptive Statistics of Plasma Concentrations
14.3.2.5	Cytisine 18 mg: Individual Data and Descriptive Statistics of Plasma Concentrations
14.3.2.6	Cytisine 21 mg: Individual Data and Descriptive Statistics of Plasma Concentrations
14.3.2.7	Cytisine 24 mg: Individual Data and Descriptive Statistics of Plasma Concentrations
14.3.2.8	Cytisine 27 mg: Individual Data and Descriptive Statistics of Plasma Concentrations
14.3.2.9	Cytisine 30 mg: Individual Data and Descriptive Statistics of Plasma Concentrations
14.3.3	Pharmacokinetic Parameters
14.3.3.1	Cytisine 6 mg: Individual Data and Descriptive Statistics of Pharmacokinetic Parameters
14.3.3.2	Cytisine 9 mg: Individual Data and Descriptive Statistics of Pharmacokinetic Parameters
14.3.3.3	Cytisine 12 mg: Individual Data and Descriptive Statistics of Pharmacokinetic Parameters
14.3.3.4	Cytisine 15 mg: Individual Data and Descriptive Statistics of Pharmacokinetic Parameters
14.3.3.5	Cytisine 18 mg: Individual Data and Descriptive Statistics of Pharmacokinetic Parameters
14.3.3.6	Cytisine 21 mg: Individual Data and Descriptive Statistics of Pharmacokinetic Parameters
14.3.3.7	Cytisine 24 mg: Individual Data and Descriptive Statistics of Pharmacokinetic Parameters
14.3.3.8	Cytisine 27 mg: Individual Data and Descriptive Statistics of Pharmacokinetic Parameters
14.3.3.9	Cytisine 30 mg: Individual Data and Descriptive Statistics of Pharmacokinetic Parameters

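### Do the adverse event tables by system organ class and preferred term lose the split by dose level?

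*SAP*

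**What the plan says.** Three sentences in SAP Section 8.7.1 bear on how treatment-emergent adverse events (TEAEs) are grouped:

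- The general sentence: "TEAEs will be presented by dose level".
- The SOC/PT sentence, later in the same paragraph: "Frequencies of TEAEs will be presented by SOC and PT, by Test product and placebo and overall".
- The severity sentence, at the end of the section, which adds frequencies by severity class "and by investigational product and dose, for all causalities" and again for related events.

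Section 8 sets the default for all summaries. For counts and percentages it says "Categorical variables will be summarized with number of subjects and percentage within a treatment (dose level"), and then "Summaries will be provided for each dose level/treatment", with placebo listed as one group beside the individual cytisine doses.

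On layout, Section 3.2 says that tables, figures and listings will be "prepared as described in the TFL shells within this SAP". The titles in Section 9.1.1 (Tables G.1, G.2, 14.2.1.3 and 14.2.1.4, and the two headed "Summary of Treatment Emergent Adverse Events by Severity") state no columns.

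**The concern.** The SOC/PT sentence is the only one specific to that table, and it names the test product, placebo and overall, but not dose. The severity sentence in the same section does name dose, so the authors evidently wrote it when they had it in mind. A programmer who applies the usual rule that a specific instruction overrides a general one could build a table with a single cytisine column.

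That would matter here. Tolerability and safety is the primary objective (Section 4.1), and the secondary objective concerns dose-limiting adverse events (Section 4.2). A table that merges nine doses cannot show whether a given preferred term becomes more frequent as the dose rises, and an event concentrated at one dose would be diluted by the subjects at the other eight.

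**Working it through.** **Denominators.** Section 5.1 allocates subjects within each dose level "in a 3:1 ratio (6 cytisine:2 placebo"), and nine dose levels are planned.

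- Total: 9 × 8 = 72, which reproduces the enrolment figure in Section 5.2.
- Cytisine: 9 × 6 = 54.
- Placebo: 9 × 2 = 18, and 54 + 18 = 72.

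**The two candidate layouts.**

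| Reading | Treatment columns | With overall |
|---|---|---|
| By dose level | 9 doses (n = 6 each) + placebo (n = 18) = 10 | 11 |
| Cytisine pooled | cytisine (n = 54) + placebo (n = 18) = 2 | 3 |

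**What pooling would do if it happened.** The event counts below are assumed. Suppose k of the 6 cytisine subjects at one dose have a given event and no other cytisine subject does. The by-dose cell is k/6 and the pooled cell is k/54.

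| k | k/6 | k/54 |
|---|---|---|
| 1 | 16.7% | 1.9% |
| 3 | 50.0% | 5.6% |
| 6 | 100% | 11.1% |

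The ratio is always 54/6 = 9. This follows from pooling nine equal groups and says nothing about whether the plan pools them.

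**Which layout the text requires.** Test each layout against each statement.

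| Statement | Dose columns, placebo, overall | Pooled cytisine only |
|---|---|---|
| 8.7.1, general sentence | met | not met by this table |
| 8.7.1, SOC/PT sentence | met: every dose column is test product | met |
| 8, percentages within dose level | met | not met |
| 8, summaries for each dose level | met | not met |

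Only the by-dose layout satisfies all four. A total cytisine column could be added to it without conflict. The two Section 8 rules carry no exception of their own: the qualifier about being otherwise indicated is attached in that section to the sentence on numerical variables and to the one on comparisons between cohorts.

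**Who decides the columns.** Under Section 3.2 the programmer works from the shells. These are blacked out in the public copy, so they can be counted neither as a gap nor as evidence for either layout.

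**The case for a change.** The best case for a change runs as follows.

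- The SOC/PT sentence departs from the formula used for demographics and medical history (Sections 8.3 and 8.4), which group by treatment plus an overall column. Substituting test product and placebo looks deliberate.
- Section 5.4 contrasts test with placebo and mentions no dose.
- The other outputs compensate only in part. Section 8.7.1 does not say that the severity tables are split by SOC and PT, and Listing 16.2.5.6 gives individual data and is not a summary.
- Section 3 requires deviations from the SAP to be justified in the study report, so unclear text blurs what counts as a deviation.

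Part of this stands. The wording is uneven, and the severity tables and the listing would not fully replace an SOC/PT table by dose.

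The rest is weaker. Section 5.4 describes randomization within a cohort, where the test product is that cohort's single dose, so it gives no support for merging doses. A change of phrase does not cancel a grouping rule stated earlier in the same paragraph. A table with dose columns is not a deviation, because the general sentence and Section 8 both call for it. The severity sentence can also be read as promising frequencies by product and dose in their own right, although this is not certain.

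**Conclusion.** The mismatch is real but editorial. The SOC/PT sentence omits a grouping that its own paragraph and Section 8 already supply, and an analyst reading the section as a whole would produce dose-level columns with pooled placebo and an overall column. On that reading the numerical effect is nil. The ninefold dilution arises only if one sentence is lifted out of context, and the percentages that illustrate it rest on assumed event counts. No stated figure, denominator or conclusion in the SAP is shown to be wrong.

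Rewording would only repeat what the plan already says elsewhere, so nothing is gained by a change. This conclusion assumes that the shells, which cannot be seen here, follow the dose-level rule of Section 8.

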### 8.7.2. Laboratory Data

Individual laboratory test data will be listed. A listing of the values outside the pre-specified ranges will be flagged (“H” - high or “L” - low) and classified regarding clinical relevance.

A decision regarding whether a result outside the reference range is of clinical significance or not was made by the clinical investigator and reported and annotated accordingly. Clinically significant abnormalities occurring during the study will be recorded as AEs.

The reference ranges for the site’s laboratory parameters will also be entered in the database and filed in the Investigator site file.

### 8.7.3. Vital Signs

Continuous vital signs monitoring (heart rate, respiratory rate and pulse oximetry) will be performed from pre-dose up to 6 hours post-dose. No listing of these data will be provided. Clinically relevant abnormalities during the period of continuous monitoring will be reported as AEs.

Vital signs (systolic blood pressure (SBP), diastolic blood pressure (DBP), pulse rate and body temperature) will be assessed at the following time points: Day 1 pre-dose, again at approximately 2, 4 and 6 hours post-dose on Day 1, and at discharge on Day 2.

Individual vital signs results will be listed. Out of range values will be flagged (“H” - high or “L” - low) and classified regarding clinical relevance. Clinically relevant abnormalities will be reported as AEs.

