### 8.7.4. Electrocardiograms

The ECG results will be listed per subject as “normal” or “abnormal”. All abnormalities will be classified in terms of clinical relevance (CR, NCR). Clinically relevant abnormalities will be reported as AEs.

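### The SAP promises by-dose summaries of safety endpoints and defines a pre-dose baseline, but plans only listings for scheduled vital signs, laboratory and ECG data; every planned safety-data table concerns adverse events.

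*SAP*

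**What the plan says.** Section 8 makes a general commitment: "Summaries of demographics, baseline characteristics and safety endpoints will be provided for the Safety Analysis Set". It adds that "Summaries will be provided for each dose level/treatment", with placebo as one of the groups. It sets the default statistics for numerical variables, states that "Baseline for post-dose assessments is defined as the last observation recorded before dose", and rules that, with limited exceptions, "unscheduled measurements will be excluded from the descriptive statistical analysis". Section 6.1 counts laboratory tests, vital signs and the 12-lead ECG among the safety variables.

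The specific sections plan less:

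- Section 8.7.2: "Individual laboratory test data will be listed", with high/low flags and a judgement of clinical relevance.
- Section 8.7.3: "Individual vital signs results will be listed", again with flags and a relevance judgement. Scheduled times are pre-dose, about 2, 4 and 6 hours after dosing, and discharge on Day 2. Continuous monitoring data are not listed at all.
- Section 8.7.4: ECGs are listed as normal or abnormal, with abnormalities classed as clinically relevant or not.

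The output list in Section 9.1 follows the specific sections. The in-text safety tables are G.1 and G.2. The end-of-text safety outputs are 14.2.1.1 to 14.2.1.6, for example "Summary of Treatment Emergent Adverse Events by Severity". Laboratory, vital-sign and ECG data appear only in listings 16.2.6, 16.2.7 and 16.2.8.

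**The concern.** The general and specific parts of the plan lead to different reports. A programmer following Section 8 would tabulate safety measurements by dose with change from baseline; one following Sections 8.7.2 to 8.7.4 and the output list would produce none of this.

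This bears on the primary objective (Section 4.1), the tolerability and safety of a single oral dose. Under the output list, a measured safety variable reaches a by-dose table only if the investigator judges an abnormality clinically relevant and it is recorded as an adverse event. A modest rise in blood pressure or pulse that grows with dose but stays within the reference range, or that is judged not relevant one subject at a time, would lie scattered through the listings. Placebo would never be used as a comparator for these measures.

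**Working it through.** The plan gives no figure to reproduce. The check compares its parts and then sizes the gap.

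**1. Planned safety outputs.** In-text: G.1 and G.2, both on treatment-emergent adverse events. End-of-text: 14.2.1.1 to 14.2.1.6, all on adverse events. That is 2 + 6 = 8 outputs, of which 0 concern laboratory, vital-sign or ECG data. All planned figures (in-text A to D; end-of-text 14.3.4 and 14.3.5) are pharmacokinetic. The table shells are redacted, but the titles in Section 9.1 are visible, so the count does not depend on hidden text.

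**2. Use of the defined baseline.** Tables F.1 to F.3 and 14.1.1 to 14.1.5 report demographics, smoking history, expired CO and medical history collected at screening. Section 8.8 does not baseline-adjust plasma concentrations, and Sections 8.9 and 8.10 use Cmax and Tmax directly. No planned table or figure shows a change from baseline.

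**3. Whether the general promise is overridden.** In Section 8 the proviso allowing exceptions governs the choice of statistics for numerical variables and, separately, comparisons between cohorts. The sentence promising safety summaries has no such proviso, and Sections 8.7.2 to 8.7.4 do not say that summaries are omitted.

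**4. Amount of data outside any summary.** Inputs: 9 cohorts of 8 (Section 5.2), 6 cytisine and 2 placebo per cohort (Section 5.1), 4 post-dose times and 4 vital-sign variables (Section 8.7.3).

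- Subjects: 9 × 8 = 72, of whom 9 × 6 = 54 on cytisine and 9 × 2 = 18 on placebo.
- Post-dose values: 72 × 4 × 4 = 1,152 (54 × 16 = 864 cytisine; 18 × 16 = 288 placebo).

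**5. What summaries could show.** The half-width of the 95% CI of a mean, in SD units, is t(0.975, n − 1)/√n.

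- One dose, n = 6: t(0.975, 5)/√6 = 1.049, about 1.05 SD.
- Pooled placebo, n = 18: t(0.975, 17)/√18 = 0.497, about 0.50 SD.

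No SD or baseline mean is assumed. A single dose group is imprecise; the value lies in seeing nine ordered doses beside placebo.

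**6. Illustration.** Table 2 gives 90 to 120 mmHg as the reference range for systolic pressure. A hypothetical rise from 105 to 119 mmHg raises no flag. If it occurred in most subjects at the higher doses, no planned table would show it.

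**The case against.** The strongest reply is that there is no real contradiction. The SAP never defines safety endpoints, and Section 6.1 uses a different term, safety variables, which also covers pregnancy tests, drug screens and physical examination. If the promise covered everything in Section 6.1, by-dose summaries of those would be due too. On a narrower reading, adverse events are the summarised endpoint, the specific sections say how other data are presented, and these agree with the output list. The rule on unscheduled measurements could equally serve the plasma concentrations. The inconsistency could also be removed by narrowing Section 8.

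Part of this stands. The unscheduled-measurement rule alone is weak evidence, and Section 8 could be narrowed. Expired CO, also a safety variable in Section 6.1, is tabulated, although as screening data. But the narrow reading leaves the baseline definition with no use anywhere. It also leaves the substance unanswered: narrowing the wording would make the text consistent and still leave the primary objective with no by-dose view of measured safety data.

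Two limits are fair. Only vital signs have post-dose times stated in the SAP, so the laboratory and ECG part depends on what post-dose assessments exist. The 1,152 values will be listed and flagged; the count shows how much goes unsummarised, not a bias. Section 9.1.1 does allow other relevant tables in the report body, but that commits to nothing.

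**Conclusion.** The concern holds. Section 8 promises by-dose safety summaries and defines a baseline for them; the specific sections and the visible output list deliver neither for laboratory, scheduled vital-sign or ECG data. The 1,152 figure assumes that all nine cohorts fill and every scheduled measurement is taken; the inconsistency does not depend on it. Clinically relevant abnormalities are still counted as adverse events, so what is lost is the sight of smaller or non-flagged dose-related shifts and their comparison with placebo. This should be corrected, but it does not invalidate the adverse-event or pharmacokinetic analyses.

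**What to change.** Add the following to Sections 8.7.2 to 8.7.4 and to output list 14.2, by dose level and pooled placebo, descriptive only and under Section 8's existing rule on unscheduled values:

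- Observed value and change from the Section 8 baseline for systolic and diastolic pressure, pulse rate and body temperature at each scheduled time in Section 8.7.3 (change at post-dose times only).
- Number and percentage of subjects with a high- or low-flagged vital sign at each time.
- Low/normal/high shift tables or flag counts for laboratory data, where scheduled post-dose values exist.
- Counts of ECG results as normal, abnormal not clinically relevant, or abnormal clinically relevant, where post-dose ECGs exist.

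The cost is a few tables and modest programming. The source datasets (ADVS, ADLB, ADEG) are already planned in Section 7.3, and the first two items need no new data. Section 3 has the SAP finalised before database lock and unblinding; tables specified by then are prespecified, whereas later ones would have to be identified in the report as additional analyses. If the sponsor prefers listings only, Section 8 must say so and drop the unused baseline definition, but that gives up the by-dose view.
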